6.2.3 Concomitant medications that must be withheld prior to the trial visits

Concomitant medication will be taken as prescribed during the trial but must be withheld prior to each visit as per Table 4 below.

Table 4: Medication-withholding periods

Medication	Time interval from last dose until spirometry
Inhaled mannitol/control (Visit 1 onwards)	6 to 24 hours
Short-acting bronchodilators (isoproterenol, isoetharine, metaproterenol, salbutamol, albuterol, levalbuterol, terbutaline) (e.g., ██████████ [®]) Short-acting anticholinergics including combination therapies e.g., ipratropium (e.g., ██████████ [®])	6 hours (minimum)
Long acting β 2 agonists including combination therapies e.g. salmeterol; eformoterol (e.g. ██████████ ██████████) Long acting anticholinergics e.g. tiotropium (e.g., ██████████)	12 hours (minimum)
Oral bronchodilators e.g.. Theophylline and β -agonist tablets	12 hours (minimum)

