Two weeks after visit 1, the Investigator or designate, will telephone the subject to:

- Collect information on any adverse events experienced (including pulmonary exacerbations or hemoptysis);
- Collect information on current concomitant medications;
- Remind the subject to adhere to withholding periods;
- Discuss adherence to trial treatment; Is this subject continuing with the IMP treatment? If the answer is NO but the subject is continuing their participation in the trial, please schedule an IMP discontinuation visit (within 2 weeks after IMP discontinuation);
- Remind the subject to return all trial drug (whether used or unused) at the next clinic visit; *and*
- Remind the subject to complete all relevant sections of the subject diary and to bring the diary to each visit.

8.1.2.3 📞 Phone call 2 weeks before visit 2 (Week 4 ± 3 days)

Two weeks before visit 2, the Investigator or designate, will call the subject to:

- Collect information on any adverse events experienced (including pulmonary exacerbations or hemoptysis);
- Collect information on current concomitant medications;
- Confirm attendance to next clinic visit;
- Remind the subject to adhere to withholding periods;
- Discuss adherence to trial treatment; Is this subject continuing with the IMP treatment? If the answer is NO but the subject is continuing their participation in the trial, please schedule an IMP discontinuation visit (within 2 weeks after IMP discontinuation);
- Remind the subject to return all trial drug (whether used or unused) at the next clinic visit; *and*

- Remind the subject to complete all sections of the subject diary and to bring the diary to each visit.

8.1.2.4 Visit 2

Visit 2 should occur on completion of 6 weeks trial treatment (± 7 days)

Prior to the visit, confirm medication-withholding periods have been adhered to. If not, the subject's visit should be postponed.

The following procedures will be performed:

- Review subject diary.
- Review concomitant medications and adverse events (including pulmonary exacerbations or hemoptysis);
- Complete ease of expectoration VAS and respiratory domain of the CFQ-R questionnaire;
- Conduct physical examination (chest sounds, weight, BP, HR, O₂ saturation, temperature, respiratory rate);
- Perform pre-mannitol pulmonary function testing (FEV₁, FVC, PEF, FEF₂₅₋₇₅);
- Dispense IMP and bronchodilator according to randomization schedule;

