8.2.1.1 Pulmonary function tests (Spirometry)

Perform all trial spirometry according to the American Thoracic Society / European Respiratory Society (ATS/ERS) criteria [12], using a standardized spirometer that meets ATS/ERS requirements and using a trained, experienced, qualified technician. **Pharmaxis or designee must approve all trial staff responsible for performing spirometry prior to the staff being delegated this task.**

Perform all lung function measures using the same spirometer throughout the trial. Perform spirometry at the same time of day for each visit (± 1 to 2 hours where possible). All visits should coincide with the trough treatment effect – that is, approximately 6 to 24 hours following the previous inhaled mannitol dose. Subjects must refrain from smoking within 1 hour of testing, consuming alcohol within 4 hours of testing, and performing vigorous exercise within 30 minutes of testing. Concomitant medications must be withheld prior to spirometry according to Table 4.

Complete spirometry after the physical exam, but prior to administration of any bronchodilator.

Seat the subject for the procedure unless they are obese, in which case testing in the standing position is preferred.

It is important that the subject is carefully instructed. Trial staff should demonstrate the appropriate technique and perform the procedure as described in Figure 4.

[figure not shown]

Figure 4: Procedures for recording forced vital capacity. Reproduced from [12]

Results of testing must meet the ATS/ERS criteria for the number of trials, acceptability and repeatability (see Table 6). The acceptability criteria should be applied before the repeatability criterion is checked.

Table 6: ATS/ERS Criteria for acceptable spirometry [12]

ATS/ERS criterion	
Number of trials	
> 3 acceptable FVC maneuvers
 
If more than eight attempts are made with the subject unable to perform a single acceptable maneuver, then discontinue testing.
 
In some cases, testing can be continued after additional instruction and demonstration, where the subject's clinical condition and tolerance allow.

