10.1.2.2 Per protocol (PP) analysis set

The per protocol analysis set consists of all randomized subjects, who have:

- Strictly met all the inclusion and exclusion criteria (i.e. will exclude those subjects who have been granted an exception to be included in the trial);
- No major protocol deviations which would affect efficacy evaluations;
- Taken trial drug for at least 60% of the 26-week treatment period;
- A valid baseline FEV₁ measure; *and*
- At least two valid assessments of FEV₁ following the baseline visit (Visit 0).

The decision to include subjects in the per protocol dataset will be made prior to unblinding of the randomization schedule. For the per protocol analysis any non-valid assessments of FEV₁ will be excluded from the analysis. The validity of the FEV₁ measurements will be assessed prior to unblinding. The subject must meet the requirement for a valid baseline and two valid post-baseline FEV₁ assessments.

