## Statistical Analysis Plan

All major protocol deviations, from [REDACTED] and programmed, will be listed and summarized for the ITT set based on the [REDACTED] category and assigned subcategory. Important minor protocol deviations, including those related to trial inclusion or exclusion criteria, conduct of the trial, subject management or subject assessments, were identified at the BDRM and will be listed by [REDACTED] category and assigned subcategory.

Criteria to determine if a subject will be included in the PP set were detailed in a BDRM preparation plan together with details of the programmatic listings to be prepared. The adjusted criteria confirmed during the BDRM to determine if a subject will be excluded from the PP set were:

- Did not meet all the inclusion and exclusion criteria.
- Was randomized but did not take at least one dose of trial medication.
- Compliance to trial medication while taking trial medication <60%.
- No valid baseline FEV1 measure, where a baseline measure was considered non valid if precluded medications were not withheld as detailed in the protocol.
- Started treatment with maintenance hypertonic saline where it was considered that there was a potential for efficacy assessments to be impacted.
- Started or stopped treatment with rhDNase or maintenance antibiotics where it was considered that there was a potential for efficacy assessments to be impacted.

Further details of the rules applied to determine inclusion in the PP set will be documented in the BDRM Highlights and will be agreed and finalized prior to database lock.

Only FEV1 measurements taken in the absence of precluded medications will be considered valid. Precluded medications and required withholding periods are detailed in Table 3 (as detailed in the protocol and CRF).

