## Statistical Analysis Plan

**Table 3: Medication-withholding periods**

Medication	Time interval from last dose until spirometry
Short-acting B2 agonists (isoproterenol, isoetharine, metaproterenol, salbutamol, albuterol, levalbuterol, terbutaline)	At least 6 hours
Short-acting anticholinergics including combination therapies (e.g. ipratropium)	
Long acting B2 agonists (e.g. salmeterol or eformoterol)	At least 12 hours
Long acting anticholinergics (e.g. tiotropium)	
Oral bronchodilators (e.g. theophylline and B-agonist tablets)	At least 12 hours

Any precluded medications taken not in accordance with the above withholding periods were reviewed at the BDRM, and an assessment was made on the validity of the associated spirometry measurements.

At the BDRM, a local major deviation was defined for the visit if the spirometry assessment was determined to be non valid, leading to the exclusion of all the specific assessment's data collected at the visit from the PP analysis. Of note, local major deviations will not lead to the exclusion of the subject from the PP set; any derived variables based on these excluded measurements will be treated as missing data and will not be imputed for the PP analysis. Local major deviations will be flagged in the data listing of major protocol deviations, but not included in the corresponding summary table.

The finalization of protocol deviations and exclusions of subjects from the PP set and of individual visit data from the PP analysis will be made [REDACTED]

The number and percentage of subjects included in and excluded from the SAF and PP sets will be presented for the ITT set, including a breakdown of all categorized reasons for exclusion from the PP set. All reasons for each subject will be included, but each subject will only be counted once within each reason category.

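### SAP Table 3 omits, without declaring it, the protocol's 6 to 24 hour trial-drug window before spirometry, so the SAP text sends no out-of-window FEV₁ to validity review for the per-protocol analysis

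*SAP*

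**What the plan says.** Protocol 6.2.3, Table 4, lists what must be withheld before spirometry. Its first row is "Inhaled mannitol/control (Visit 1 onwards"), with an interval of 6 to 24 hours. Protocol 8.2.1.1 gives the reason: every visit should fall at the trough of the treatment effect, "that is, approximately 6 to 24 hours following the previous inhaled mannitol dose". Protocol 8.1.2.4, 8.1.2.7 and 8.1.2.11 (Visits 2 to 4) each instruct: "Prior to the visit, confirm medication-withholding periods have been adhered to. If not, the subject's visit should be postponed".

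Protocol 10.1.2.2 says "For the per protocol analysis any non-valid assessments of FEV₁ will be excluded from the analysis" and leaves validity to be judged before unblinding, without defining it. Among its conditions for PP membership is "Taken trial drug for at least 60% of the 26-week treatment period".

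SAP 5.5 supplies the missing definition. An FEV₁ is valid only if no precluded medication was on board, and the reference list is Table 3: "Precluded medications and required withholding periods are detailed in Table 3 (as detailed in the protocol and CRF"). The text after the table adds: "Any precluded medications taken not in accordance with the above withholding periods were reviewed at the BDRM". A reading judged non-valid becomes a local major deviation. It is dropped from the PP analysis and not imputed.

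**The concern.** Table 3 claims to carry over the protocol's withholding periods, but the trial-drug row is missing. It was the only row with an upper limit. Blinded review at the BDRM is triggered by departures from Table 3, so time since the last trial dose triggers nothing. SAP Section 11 declares in item 3 that the PP criteria were adjusted and local major deviations introduced, but it does not mention this row.

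The interpretation of the PP analysis is at stake. Protocol 10.2.6 says it estimates the effect of taking mannitol, as distinct from being randomized to it, and SAP 8.1.3.1 uses it as a robustness check on the ITT result. If FEV₁ values taken well outside the trough window count as valid, the PP estimate moves toward the ITT estimate, and agreement between the two says less.

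**Working it through.** The plan gives no figure on this point to reproduce. The check is a comparison of the two tables, followed by date arithmetic and an illustration of size.

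**1. The two tables side by side.**

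| Item | Protocol Table 4 | SAP Table 3 |
|---|---|---|
| Trial drug (mannitol or control) | 6 to 24 hours | absent |
| Short-acting bronchodilators and anticholinergics | 6 hours minimum | at least 6 hours |
| Long-acting β2 agonists and anticholinergics | 12 hours minimum | at least 12 hours |
| Oral bronchodilators | 12 hours minimum | at least 12 hours |

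The bronchodilator rows carry the same intervals. Only the trial-drug row is gone.

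**2. Which limit is lost.** Protocol 6.1 requires a bronchodilator 5 to 15 minutes before every trial dose. A trial dose taken less than 6 hours before spirometry would therefore usually also breach the 6-hour bronchodilator row, so the lower limit is largely recovered. No row of Table 3 has an upper limit, so nothing replaces the 24 hours.

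**3. Other routes for off-drug FEV₁ into the PP analysis.** SAP 6.2.7 bases all efficacy analyses on both on- and off-treatment data. SAP Table 6 marks off-drug data as included for Primary - Supportive 1, the PP analysis. SAP 5.5 excludes for compliance below 60% measured only up to the last dose (formula in SAP 9.2), so an early stopper can stay in the PP set. For example, someone who takes every capsule for 14 days scores 280 / (20 × 14) = 100%.

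**4. Gap from last dose to FEV₁.** Gap = visit target day (SAP Table 4: Days 43, 99 and 183, with the last window ending on Day 211) minus day of last dose.
- Protocol exposure rule: 60% of 182 days = 109.2 days. Last dose on Day 110 gives a Week 26 gap of 183 − 110 = 73 days, or 211 − 110 = 101 days at the end of the window.
- SAP compliance rule: last dose on Day 14 gives 43 − 14 = 29, 99 − 14 = 85 and 183 − 14 = 169 days.

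Long gaps are possible under either membership rule, and much longer ones under the SAP's.

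**5. Illustrative size.** Inputs: an 80 mL effect with no change on control (Protocol 10.1.1); full return to baseline after stopping (the premise in SAP 6.3); equal weight on three visits (SAP 8.1.1). The documents give no stopping fraction, so p is assumed. With k post-baseline visits after stopping:

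diluted effect = 80 × (1 − p × k/3)

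| Stop near | Exposure | k | p = 5% | p = 10% | p = 20% |
|---|---|---|---|---|---|
| Week 16 | 16/26 = 62% | 1 | 78.7 mL | 77.3 mL | 74.7 mL |
| Week 8 | 8/26 = 31% | 2 | 77.3 mL | 74.7 mL | 69.3 mL |

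Only the Week 16 row meets the protocol's 60% rule. The Week 8 row arises only under the SAP's changed compliance criterion.

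**The case against.** The strongest reply is that off-drug FEV₁ is in the PP analysis by explicit choice, not through a missing table row. SAP 6.2.7 and Table 6 say so, and SAP Section 11 discloses that the PP criteria were adjusted. A reader might infer that the omitted row is itself what lets FEV₁ from weeks or months after the last dose into the PP analysis, and that putting it back would cure this. The documents do not support that. Restoring the row alone would trigger review, not exclusion, and would leave Table 3 in conflict with Table 6. Nor do the Week 8 figures measure the omission, because such a subject fails the protocol's 60% rule and is present only through the compliance criterion.

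Further, the protocol never says that FEV₁ beyond 24 hours is non-valid. The window is approximate and serves visit scheduling. Postponing a visit makes no sense for someone permanently off drug, and Protocol 9.2 asks discontinuers to attend all remaining visits. A list of precluded medications is also a natural place for drugs whose presence contaminates a reading, less so for an upper limit on time since trial drug.

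The on-drug question is partly answered elsewhere: Supportive Analyses 6 to 8 drop data more than 7 days after discontinuation. The CRF and the BDRM Highlights are not available, and a drug-timing check may sit there.

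These points limit cause and size, but they do not remove the mismatch. The SAP says its table follows the protocol, the trial-drug row is absent, the change is undeclared, and no SAP text sends a breach of the trough window to validity review. Supportive Analyses 6 to 8 use the ITT set and a 7-day limit, so they neither repair the PP analysis nor apply the trough window.

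**Conclusion.** The point stands as an undeclared departure from the protocol that should be corrected. It leaves the protocol's spirometry window, chiefly its 24-hour limit, unchecked in the one analysis meant to show the effect of taking mannitol. It is one of several provisions with that result, so they need reconciling together.

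Under the protocol's exposure rule the illustrative loss is 1.3 to 5.3 mL of 80 mL. That rests on assumed stopping fractions of 5% to 20%, complete loss of effect after stopping, and attendance at Week 26. A reader might infer that the PP estimate is materially distorted or that the primary result is in doubt. The documents support neither: the ITT analysis deliberately uses all data regardless of adherence and does not depend on Table 3.

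**What to change.** Before unblinding:
- Restore the trial-drug row to SAP Table 3 as it stands in Protocol Table 4, so that post-baseline spirometry outside the window is flagged for blinded validity review.
- State that FEV₁ after permanent discontinuation is not valid for the PP analysis, and align SAP 6.2.7 and the PP row of Table 6 with that.
- Revisit the compliance criterion in SAP 5.5 at the same time, since it decides how many early stoppers are in the set.
- If the team prefers the current approach, declare and justify it in Section 11 and stop describing Table 3 as matching the protocol.

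This takes one table row, one programmed check and a few aligned sentences. For permanent stoppers the check can use the recorded date of last trial medication. For isolated missed doses the diary records dates only (Protocol 6.1). With twice-daily dosing, dates can prompt review but cannot establish a 24-hour breach.

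There are two statistical costs. The PP confidence interval widens slightly. Excluded values are not imputed, so the PP mixed model leans on missing-at-random and can carry an on-drug benefit forward, which the SAP adopted baseline carry-forward to prevent. The PP result should therefore be read beside Supportive Analyses 6 to 8. The ITT primary analysis does not change.

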## Statistical Analysis Plan

**Table 3: Medication-withholding periods**

Medication	Time interval from last dose until spirometry
Short-acting B2 agonists (isoproterenol, isoetharine, metaproterenol, salbutamol, albuterol, levalbuterol, terbutaline)	At least 6 hours
Short-acting anticholinergics including combination therapies (e.g. ipratropium)	
Long acting B2 agonists (e.g. salmeterol or eformoterol)	At least 12 hours
Long acting anticholinergics (e.g. tiotropium)	
Oral bronchodilators (e.g. theophylline and B-agonist tablets)	At least 12 hours

Any precluded medications taken not in accordance with the above withholding periods were reviewed at the BDRM, and an assessment was made on the validity of the associated spirometry measurements.

At the BDRM, a local major deviation was defined for the visit if the spirometry assessment was determined to be non valid, leading to the exclusion of all the specific assessment's data collected at the visit from the PP analysis. Of note, local major deviations will not lead to the exclusion of the subject from the PP set; any derived variables based on these excluded measurements will be treated as missing data and will not be imputed for the PP analysis. Local major deviations will be flagged in the data listing of major protocol deviations, but not included in the corresponding summary table.

The finalization of protocol deviations and exclusions of subjects from the PP set and of individual visit data from the PP analysis will be made [REDACTED]

The number and percentage of subjects included in and excluded from the SAF and PP sets will be presented for the ITT set, including a breakdown of all categorized reasons for exclusion from the PP set. All reasons for each subject will be included, but each subject will only be counted once within each reason category.

## Statistical Analysis Plan

### 6. GENERAL ASPECTS FOR STATISTICAL ANALYSIS

#### 6.1. GENERAL METHODS

Unless otherwise specified, all demographic and baseline data will be presented by treatment group and overall. Efficacy and safety data will be presented by treatment group. All subjects entered into the database will be included in subject data listings.

Continuous variables will be summarized using the number of observations (n), n missing (n miss), mean, SD, median, minimum, and maximum. Categorical variables will be summarized using the number (n) and percentage (%) of subjects with non-missing data per category. Where relevant, the number of missing values will be included as a "Missing" category. Unless otherwise specified, the denominator for each percentage will be the number of non-missing observations within the analysis set and treatment group.

All tests of hypotheses will be 2-sided and conducted at the 5% significance level, and all confidence intervals (CIs) will be 2-sided at the 95% level.

#### 6.2. KEY DEFINITIONS

##### 6.2.1. Dates of First and Last Trial Medication Intake

In this document, trial medication refers to the randomized trial medication (inhaled mannitol [400 mg b.i.d.] and control [50 mg inhaled mannitol b.i.d.]) and does not include the MTT.

The date of first trial medication is taken as the date of first administration of trial medication after randomization.

The date of last trial medication is taken as the date of last administration of trial medication.

If date of last administration of trial medication is missing, the date will be imputed using the last available known start or end date of trial medication.

## Statistical Analysis Plan

### 6.2.2. Trial Day

Trial day is defined as the number of days from the date of randomization to the event date and will be calculated as follows:

- If the event date  $\geq$  date of randomization, trial day = event date - date of randomization + 1. Trial Day 1 is therefore defined as the day of randomization.
- If the event date  $<$  date of randomization, trial day = event date - date of randomization.

### 6.2.3. Treatment Day

Treatment day is defined as the number of days from the date of first dose to the event date and will be calculated as follows:

- If the event date  $\geq$  date of first dose, treatment day = event date - date of first dose + 1. Treatment Day 1 is therefore defined as the day of first dose.
- If the event date  $<$  date of first dose, treatment day = event date - date of first dose.

### 6.2.4. Baseline

The baseline value for all efficacy endpoints will be taken as Visit 1. It will be assumed that assessments performed on this visit were prior to first trial medication administration, with the exception of post-dose spirometry. Therefore, efficacy baseline will be the Visit 1 measurement unless the Visit 1 measurement is missing, where the Visit 0 measurement will be used as baseline.

The baseline value for safety endpoints (vital signs and physical examination) will be taken as the latest available measurement prior to or on Treatment Day 1 (i.e. day of first trial medication dose). It will be assumed that safety assessments performed on Treatment Day 1 were prior to trial medication administration. Baseline will be the Visit 1 measurement.

